7.1 Acupuncture

The acupoints of bilateral Shenshu (BL23), “Dachangshu (BL25)”, Weizhong (BL40), Chengshan (BL57), and Taixi (KI3) will be acupunctured. The locations of all acupoints except “BL25” will be based on the World Health Organization (WHO) Standard Acupuncture Locations [21], as displayed in Table 1. “BL25” is located at 1.5 Bone-cun horizontally outward to the spinous process of the fourth lumbar vertebra.

Participants will lie in the prone position and relax. A pillow will be placed under the lower abdomen of the participants, and their hands will be raised above their heads in order to maximize the enlargement of the intervertebral foramen. Prior to acupuncture, 75% alcohol pads will be used to sterilize the skin around the acupuncture points. For “BL25,” sterile disposable steel needles (0.3 mm × 75 mm) will be inserted directly to a depth of 50-70 mm until participants feel a sensation similar to electric shock radiating downward to the knees and the posterior lower legs. Then, the needle will be lifted upward for 1-2 mm without manipulation during the treatment. For the other four acupoints (BL23, BL40, BL57, and KI3), the needles (0.3 mm × 40 mm) will be inserted to a depth of 15-30 mm depending on participants’ somatotype, gently rotated and lifted three times to achieve the sense of sourness, distention, and heaviness (*deqi*) [22]. It should be noted that the needle at KI3 will be inserted at an angle of 45° obliquely downward. The needles at all points will be retained for 30 minutes with light lifting, thrusting, and twirling every 10 min during each session. Participants will receive 18 treatment sessions given 3 times per week (ideally every other day) for 6 continuous weeks.

Table 1. Summary of the Acupoints’ Location

Acupoints	Location	Depth of insertion
Shenshu (BL23)	In the lumbar region, at the same level as the inferior border of the spinous process of the second lumbar vertebra (L2), 1.5 Bone-cun* lateral to the posterior median line.	15-30 mm
“Dachangshu (BL25)”	In the lumbar region, at the same level as the spinous process of the fourth lumbar vertebra (L4), 1.5 Bone-cun lateral to the posterior median line.	50-70 mm
Weizhong (BL40)	On the posterior aspect of the knee, at the midpoint of the popliteal crease.	15-30 mm
Chengshan (BL57)	On the posterior aspect of the leg, at the connecting point of the calcaneal tendon with the two muscle bellies of the gastrocnemius muscle.	15-30 mm
Taixi (KI3)	On the posteromedial aspect of the ankle, in the depression between the prominence of the medial malleolus and the calcaneal tendon.	15-30 mm

1 Bone-cun ≈ 20 mm

7.2 Sham Acupuncture (SA)

For the SA group, needles of the same size (0.3 mm ×40 mm) will be inserted at the same acupoints used in treatment of the acupuncture group to a depth of 2-3 mm. No manipulation of needles will be conducted. The treatment duration and frequency of sessions for participants in the SA group will be the same as in the acupuncture group.

7.3 Standardization of Treatment

Guang'anmen Hospital will supply single-use, sterile, and disposable acupuncture needles for each participating site.

Two certified acupuncturists will be needed in each site to perform all the treatments, while the 18 sessions of treatment for each participant should be completed by one specific acupuncturist. All acupuncturists in this trial are required to have completed their professional training in acupuncture in universities of Chinese medicine with at least 2 years of clinical experience.

To improve the consistency of treatments, acupuncturists at each site will receive trial-specific (standardized operation procedure) training at the project launching session. The training will include detailed acupuncture points locations and manipulation methods in both the acupuncture and SA groups. A video showing detailed information on how to perform the acupuncture and SA will also be provided.

To avoid the inadvertent unblinding, acupuncturists will not tell anyone else the treatment allocation. The contacts between acupuncturists and participants should be as short as possible.

The acupuncturists will be instructed to follow standardized operating procedure:

Step 1:

The participant is piloted by research assistant to hospital bed, which was screened-off separately one-by-one. Their companions will be guided to wait outside the clinic, if any. Acupuncturist instructs the patient to lie prone on the bed, with lumbosacral and lower shin areas exposed, and tell the participant that a 30-minute treatment will be given.

Before the first session of treatment, participants will be told that they may receive either the traditional acupuncture or minimal acupuncture group, and they may not have sensation during the 30-minute retention of acupuncture needles out of body adaptation.

Step 2:

After sterilization, the acupuncturist will start to conduct administration according to treatment protocol. The acupuncture group will receive deep insertions of needles at acupoints, while the SA group will receive superficial insertions of needles at same acupoints.

Step 3:

After insertion of needles at appropriate areas, the acupuncturist will gently rotate, lift and thrust three times at each acupoint (except “BL25”) to achieve the sense of sourness, distention, and heaviness (*deqi*), while no manipulation will be made in the SA group.

Step 4:

After 10 minutes, the acupuncturist will conduct the second needle manipulation in the acupuncture group, which involves light lifting, thrusting, and twirling three times at each acupoint (except “BL25”). In contrast, no manipulation will be made in the SA group.

Step 5:

After another 10 minutes, acupuncturist will conduct the third needle manipulation by light

lifting, thrusting, and twirling three times at each acupoint (except “BL25”) in the acupuncture group, while no manipulation will be made in the SA group.

Step 6:

After another 10 minutes, acupuncturist will remove the needles.

7.4 Permitted and Prohibited Concomitant Treatments

The use of medications or other therapies specific for symptoms of DLSS will be discouraged during this trial. Patients with intolerable pain will be allowed to take 200 mg dose of Celebrex (Pfizer China, Inc.) orally once a day for three consecutive days as rescue medicine with detailed record. We will compare the proportion of subjects using rescue medications between groups. Rescue medicine will be prohibited 48 hours prior to the pain and physical function assessment.

8. Subject Evaluation

8.1. Outcomes Measurements

8.1.1 Primary Outcomes

The primary outcome will be the change in the modified RMDQ score from baseline to week 6.

The RMDQ is a reliable pain-specific functional status questionnaire that is easy and simple for participants to complete [23]. The RMDQ includes 24 questions with a score range of 0–24. Notably, in this study, we will modify the response to “caused by low back or leg pain” for each question, which will be more suitable for participants who have sciatica [24, 25]. Disability is measured in terms of walking, standing, bending, working, sleeping, and activities of daily living. Higher scores indicate more severe symptoms, and a change in the score by 2.5 points is the minimal clinically important difference (MCID) for RMDQ scores [23]. A reduction of at least 30% and 50% reduction were additionally interpreted as minimal and substantial clinically meaningful improvement respectively [26, 27], which were adopted as secondary outcomes.

8.1.2 Secondary Outcomes

Secondary outcomes will include the following:

- (1) Changes in the RMDQ score from baseline to weeks 18 and 30;
- (2) The proportion of participants having at least 30% and 50% reductions in the RMDQ score from baseline to weeks 6, 18, and 30;
- (3) Changes in the average pain scores for the buttocks and/or legs when walking, standing, or extending the back as measured by the NRS in the previous 1 week from baseline to weeks 6, 18, and 30.

The NRS is a concise scale for assessing pain that is completed by the participants themselves. NRS scores range from 0 to 10 with 11 grades, and higher scores indicate greater pain [28, 29]. Two scales including one for measuring buttock and/or leg pain and another for measuring low back pain will be used (participants should answer with the average score for the previous 1 week). The degree of pain in the bilateral legs may be different, and data collection will be based on the degree of pain in the leg with more severe pain;

- (4) The proportion of participants having at least 30% and 50% reductions from baseline in the average pain scores for the buttocks and/or legs when walking, standing, or extending the back, as measured by the NRS for the previous 1 week at weeks 6, 18, and 30;
- (5) Changes in the average pain score for the lower back when walking, standing, or extending the back, as measured by the NRS for the previous 1 week from baseline to weeks 6, 18, and 30;

- (6) Changes in the mean scores of the SSSQ for symptom severity and physical function from baseline to weeks 6, 18, and 30 and scores on the SSSQ satisfaction subscale at weeks 6, 18, and 30.

The SSSQ is a short outcome measure for symptoms and functions [30]. The SSSQ consists of 18 questions and three domains including symptom severity, physical function, and satisfaction with the degree of treatment. The scores for all three domains are calculated by taking the total score for the domain and dividing it by the number of answered questions, and if more than two items are missing, the scale scores for that domain are considered missing.

Six questions in the symptom severity domain assess pain of the back, buttocks, legs, or feet as well as pain frequency, numbness, and weakness with scores ranging from 1 to 5, while one question assesses balance with possible scores of 1, 3, and 5. Higher scores indicate worse symptoms. The physical function domain assesses walking distance and ability to walk for pleasure, shopping, and getting around the house or apartment and from the bathroom to the bedroom. This domain has five questions with scores ranging from 1 to 4, and higher scores indicate less satisfaction. The satisfaction domain has four categories (very satisfied, somewhat satisfied, somewhat dissatisfied, and very dissatisfied) with a score range of 1–4 [31, 32].

(7) The proportion of participants who are somewhat satisfied and very satisfied based on the satisfaction domain of the SSSQ at weeks 6, 18, and 30;

According to satisfaction domain of the SSSQ, patients scoring 1.5–2.5 points are regarded as somewhat satisfied with the therapy, and those scoring 1.5 points or lower are regarded as very satisfied with the therapy [33].

(8) Changes in the HADS score from baseline to weeks 6, 18, and 30.

The HADS is validated and standardized for measuring the state of anxiety and depression [34, 35]. The HADS has two subscales with 14 items (7 items each), and a total score range of 0–21 with a range of 0–3 for each item. A score of ≥ 8 indicates the presence of anxiety and/or depression.

(9) Expectancy of acupuncture

Expectancy of acupuncture will be recorded at baseline. Participants will be required to answer two questions: “In general, do you believe acupuncture is effective for treating the illness?” and “Do you think acupuncture will help to improve your symptoms of DLSS?”

(10) Blinding assessment

Patients will be asked to answer the following questions after treatment (sessions 17 or 18) within 5 min: “Do you think you have received traditional acupuncture over the past 6 weeks?” The patients can answer “yes” or “no.”

(11) Safety assessment

Adverse events (AEs) related to acupuncture include severe pain, needle breakage, fainting, local hematoma, localized infection, and post-acupuncture discomfort with symptoms such as nausea, vomiting, palpitation, dizziness, headache, anorexia, and insomnia during the treatment period. AEs irrelevant to the treatment will also be recorded in detail throughout the trial.

8.2 Evaluation Procedures

8.2.1 Schedule of Evaluation

Table 2. Enrolment, Intervention and Evaluation Schedules

	Study Period							
	Enrollment/Allocation week		Post-allocation week					
			Treatment week			Follow-up		
Timepoints	Week -1	Week 0	1	2	3	4	5	6
Enrollment								
Eligibility screen	x							
Informed consent	x							
MRI /CT	x							

Demographics	x								
Expectancy of acupuncture	x								
Allocation		x							
Interventions									
Acupuncture			x	x	x	x	x	x	
Sham acupuncture			x	x	x	x	x	x	
Assessments									
RMDQ	x						x	x	x
NRS	x						x	x	x
SSSQ	x						x	x	x
HADS	x						x	x	x
Blinding assessment							x		
Safety assessment	x		x	x	x	x	x	x	x

Abbreviations: MRI magnetic resonance imaging, CT computed tomography, RMDQ Roland-Morris Disability Questionnaire, NRS Numerical Rating Scale, SSSQ Swiss Spinal Stenosis Questionnaire, HADS Hospital Anxiety and Depression Scale

8.2.2 Baseline assessment

The demographic information and outcome assessment at baseline will be collected in Timepoint of assessment 1, which has been described in 5.2 Screening and Baseline Assessment.

8.2.3 Six-week Treatment Phase

During the 6-week treatment (weeks 1-6), Timepoint of assessment 2 will be scheduled at week 6.

Participants will complete the RMDQ, NRS, SSSQ and HADS at week 6.

Within 5 minutes after treatment (sessions 17 or 18) at the week 6, the success of blinding will be assessed by outcome assessors at hospital.

8.2.4 Twenty-four-week Follow-up Phase

During the 24-week follow-up (weeks 7-30), Timepoint of assessment 3 will be scheduled at week 18, and Timepoint of assessment 4 will be scheduled at week 30.

Participants will complete the RMDQ, NRS, SSSQ and HADS at weeks 18 and 30. We will provide a self-assessment questionnaires/scales notebook for each participant. For the results of Timepoint of assessment 3 (week 18) and Timepoint of assessment 4 (week 30), the notebook could be mailed to hospitals or submit to hospitals by participants in person.

9. Safety Assessment and Subject Withdrawal

9.1 Adverse Events

We will handle and document the adverse events (AEs) using the standard operating procedures for monitoring and reporting all AEs.

According to their potential association with the treatment, AEs will be categorized as treatment-related or non-treatment-related within 24 hours after their occurrence. Treatment-related AEs include pain, haematoma, localized infection, broken needle, fainting, nausea, headache, dizziness, insomnia, vomiting, or palpitations during or after treatment.

Serious AEs will be defined as events requiring hospitalization, causing disability or impaired ability to work, threatening life or resulting in death. Any serious AEs will be immediately reported to the principal investigator (ZL) and Medical Ethics Committee at individual clinical site and Guang'anmen Hospital within 24 hours. A research assistant will be required to record serious AEs, including information on the time of occurrence, severity, duration, measurement, management, and its outcome.

All the serious AEs and AEs will be recorded and measured by participants themselves, acupuncturists, and orthopedists through the whole trial. The participants will be followed until resolution, study completion or termination. Guang'anmen Hospital has insurance covering for harm associated with the interventions during this trial.

9.2 Subject Withdrawals

Participants may withdraw from the trial at any time at their own discretion; the investigator may also determine whether it is in the best interest of subjects to withdraw from the trial due to worsening of symptoms, or the occurrence of serious AEs.

10. Administrative Responsibilities

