3.4 Study Time Frame

The duration of the study for each participant will be 31 weeks: 1 week before randomization as eligibility screening and baseline assessment, 6 weeks of treatment period, and 24 weeks of follow up period after the cessation of treatment (Figure 1. Study Design).

[figure not shown]

Figure 1. Study Design

There will be four timepoints of assessment:

Timepoint 1 will be scheduled during weeks -1 as eligibility screening and baseline assessment;

Timepoint 2 will be scheduled at week 6 at the end of treatment period;

Timepoints 3 and 4 will be scheduled at weeks 18 and 30, respectively, during 24-week follow-up period.

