5.2 Screening and Baseline Assessment

On patients' official screening visit to hospital, they will sign the written informed consent form. Research assistants of each site will record their demographic information, course of disease and previous treatments. Orthopedists are responsible for the diagnosis and the differential diagnosis of DLSS.

Patients will receive a series of procedures to screen for eligibility, which will take approximately one week (week -1). To use the funds rationally and for consideration of the convenience of participants, the procedures will be scheduled step by step (Figure 3. Subject Flow Chart), and the eligibility criteria will be verified timely during the process. Those who fail in one step will not receive further screening.

To ensure the accuracy of eligibility screening and outcome assessment, it is imperative that patients avoid any therapy for DLSS throughout the trial. However, rescue medication can be used for emergency, except 48 hours before the assessment of pain and physical function.

The screening procedures include (in sequence):

- (1) The medical history, demographic information, and previous treatments;
- (2) Physical examinations;
- (3) RMDQ score and NRS score for the buttocks and/or legs, back;
- (4) MRI (mainly) or CT.

Participants who are still eligible after the examinations will complete the baseline outcome assessment questionnaires, which include the Swiss Spinal Stenosis Questionnaire (SSSQ), the Hospital Anxiety and Depression Scale (HADS), and participants' expectation assessment. The RMDQ and NRS will be completed again.

Note: Although the eligibility screening and baseline assessment are interpreted as Timepoint of assessment 1, participants might need to visit the hospital more than once during the process. The clinical site can arrange the procedures of examinations in accordance with the rapidity of each examination in their own hospital to save participants' time and visits to hospital.

[figure not shown]

Figure 3. Subject Flow Chart

Abbreviations: RMDQ, Roland-Morris Disability Questionnaire; NRS, Numerical Rating Scale; SSSQ, Swiss Spinal Stenosis Questionnaire; HADS, Hospital Anxiety and Depression Scale.

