6.2 Blinding

The patients, outcome assessors, and statisticians will be blinded to the treatment allocation. Only acupuncturists are aware of the group allocation to administrate treatments.

Participants in the SA group will receive minimally invasive, superficial needle insertion of 2-3mm at the same acupoints used as the acupuncture group. Treatment protocol will be similar to that of the acupuncture group, and the acupuncturists will be trained to perform the same needling rituals in both groups. To test the success of blinding, within 5 minutes after treatment (Session 17 or 18) at week 6, participants will be told that there are two kinds of acupuncture methods, which are the traditional acupuncture where the insertion is relatively deep, and the minimal acupuncture where the insertion is relatively shallow; and participants will be randomly assigned to receive traditional acupuncture or minimal acupuncture at 50% chance respectively. Participants will then be asked to answer the question that “Do you think you have received traditional acupuncture in the past weeks?” The participants will be able to choose one of the following options as the answer: “Yes” or “No”.

7. Interventions

Sterile disposable steel needles (Hwato, Suzhou, China) will be used, and acupuncturists with at least 2 years of clinical experience will supply the treatment.

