10.4.6 Data Auditing and Blinding Review

When the data checking is finished, a data auditing and blinding review meeting will be held. In the meeting, the data administrators, statisticians, researchers, clinical inspectors, and other related members will have a discussion on the following items according to the data management report and the data lists:

- Distribution of the participants;
- Protocol violation;
- Possible outlier;
- Baseline data;
- Outcomes;
- Statistical analysis plan.

Participants will be classified to their suitable statistical analysis sets according to the definition in the protocol. No patient can be excluded from the analysis, unless getting the permission of the meeting participants. All the meeting participants will sign the data locking consent, and the data auditing resolution.

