10.5 Quality Control

(1) To guarantee the quality of the study, the trial protocol will be reviewed and revised by expert acupuncturists, orthopedist, and statisticians several times.

(2) A central randomization system will be adopted to avoid selection bias.

(3) Strict eligible criteria will be pre-set to restrict the research population. The diagnosis, inclusion and exclusion criteria are designed in accordance with the guidance of NASS.

(4) Trial-specific (standardized operation procedure) extensive training will be given to all the research staff participating the trial at the project launching session. Acupuncturists will be trained on how to use the central randomization system, the standardized manipulation method, and needling rituals.

Outcome assessors will be trained how to fill the case report form. Clinical Research Assistants (CRC) will be trained to use data entry system.

(5) We will provide a self-assessment questionnaires/scales notebook for each participant. Participants will be asked to complete the notebook. During 6-week treatment period, participants will bring the notebook to hospital themselves. For the outcome assessment at weeks 18 and 30, they can mail the notebook to hospital or bring the manual to hospital themselves. The data from the notebook will be the raw data for analysis, and will be checked and recorded in CRF by outcome assessors. The double-input method will be used for data entry, and all data related to patients will be stored confidentially. The statistical analysis of the data will be calculated by independent statisticians. The participants, outcome assessors, CRC and statisticians will all be unaware of the group allocation.

(6) Participation processes in the trial of the same participants should be taken charge of by the same acupuncturist, research assistant and outcome assessor throughout the trial.

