6.3.3 Analysis for Primary Outcome

The primary analysis will be conducted a mixed effects model for repeated measures (MMRM). In this model, the observed change from baseline score at each scheduled post-baseline visit will be the dependent variable. The model will include the baseline RMDQ score as a fixed effect, with categorical factors for treatment group (acupuncture and SA), visit and treatment \times visit interactions. The interactions will remain in the model regardless of significance. Treatment group comparisons at each visit will be estimated by differences between least squares (LS) means from the treatment \times visit interaction, with accompanying *P*-values and 95% CIs. An unstructured covariance pattern will be used to estimate the variance–covariance of the within-subject repeated measures. Parameters will be estimated using maximum likelihood with the Newton-Raphson algorithm and using the Kenward–Roger method for calculating the denominator degrees of freedom.

Sensitivity Analyses for the Primary Outcome

Multiple imputation will be used to impute missing values under the missing-at random assumption (MAR). Specifically, 100 imputed data sets will be generated using the fully conditional specification method or regression method with the number of iterations set to 10 for the following variables: group, baseline value and dependent variable. After multiple imputation, each of the hundred multiple imputation datasets will be analyzed using the MMRM model. The overall estimates will be calculated using Rubin's rules. The multiple imputation procedure (PROC MI) in SAS, version 9.4 will be used and *P*-value <0.05 will be considered statistically significant. To address potential center differences, we will incorporate site as either a fixed or random effect in the MMRM model.

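### Section 9.2 does not separate stopping needling from leaving the trial, so a week-6 RMDQ can be lost because of worsening, which the MAR-only analyses cannot test; the likely effect is small and the remedy cheap

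*Combined protocol and SAP*

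**What the plan says.** - **Withdrawal (protocol 9.2).** Participants may leave when they wish. The investigator may also decide that a participant should "withdraw from the trial due to worsening of symptoms, or the occurrence of serious AEs". No separate step of stopping treatment is described, and the section is silent on later data collection.
- **Timing (protocol 3.4).** "Timepoint 2 will be scheduled at week 6 at the end of treatment period". No RMDQ is scheduled between baseline and that visit, and the change to week 6 is the primary outcome (8.1.1).
- **Remote collection.** Section 10.3(5) has outcomes of less compliant participants recorded by phone or message, and names no visit. Section 10.5(5) mentions posting the notebook for weeks 18 and 30 only. For the treatment phase it says: "During 6-week treatment period, participants will bring the notebook to hospital themselves".
- **Analysis set.** Efficacy is analysed by intention to treat in all randomised participants (SAP 6.2). Protocol 10.4.6 adds: "No patient can be excluded from the analysis, unless getting the permission of the meeting participants".
- **Analysis (SAP 6.3.3).** The primary model is an MMRM on observed changes from baseline. For missing data there is one sensitivity analysis: "Multiple imputation will be used to impute missing values under the missing-at random assumption (MAR"), using group, baseline value and the dependent variable. The other sensitivity analysis concerns centre.

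**The concern.** Worsening of symptoms is close to what the RMDQ measures, so a withdrawal on that ground depends on the outcome. If it comes before week 6 and follow-up stops, the participant has only a baseline score. He or she stays in the ITT set by name but contributes nothing to a model of observed change. The imputation knows arm and baseline, not the worsening that led to the loss, so it fills in roughly what the remaining participants in that arm achieved.

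The week-6 comparison would then shift from all randomised participants toward those who were not doing badly. The planned sensitivity analysis would agree with the primary result without having tested this. A missing week-6 score cannot be recovered later.

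**Working it through.** **The plan's own figure (protocol 11.1).** Inputs: difference 2.5, SD 5.5, two-sided 5%, 80% power, 20% dropout, 98 per arm. The normal approximation gives 76 per arm, 76/0.8 = 95, total 190. The t-based calculation gives 77 per arm, 77/0.8 = 96.25, so 97, total 194. The stated 196 is within two participants of that. Completers: 98 × 0.8 = 78.4, so 78 per arm. SE = 5.5 × √(2/78) = 0.88, and power is 81.0% (normal) or 80.5% (t).

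**Assumed inputs (none is in the documents).** True mean changes −5.5 (acupuncture) and −3.0 (sham), so the true difference is −2.5. SD 5.5. Worsening means an RMDQ rise of at least 2.5. A fraction q of worsening patients is withdrawn and not followed, with the same rule in both arms.

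**Model A: decision before week 6.** The earlier change has half the week-6 mean, SD 5.5, and correlation r = 0.5 to 0.9 with the week-6 change. For an arm with week-6 mean μ:
- a = (2.5 − μ/2)/5.5; p = 1 − Φ(a); λ = φ(a)/p
- mean week-6 change of worsening patients: w = μ + r × 5.5 × λ
- fraction lost: ℓ = q × p
- mean of those who stay: (μ − ℓw)/(1 − ℓ)

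Worked case, q = 0.25 and r = 0.5:
- Acupuncture: a = 5.25/5.5 = 0.955, p = 17.0%, λ = 1.489, w = −1.41, ℓ = 4.2%, stayers −5.68.
- Sham: a = 4/5.5 = 0.727, p = 23.4%, λ = 1.311, w = +0.61, ℓ = 5.8%, stayers −3.22.
- Difference −2.46, a shift of 0.04.

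**Model B: selection on the week-6 change itself.** Same formulas with μ in place of μ/2 and r = 1, giving p = 7.3% and 15.9%.

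| q | A: difference | A: lost (of 196) | B: difference | B: lost | Power, A | Power, B |
|---|---|---|---|---|---|---|
| 0.25 | −2.46 to −2.42 | 9.9 | −2.35 | 5.7 | 79.8% to 78.5% | 76.1% |
| 0.50 | −2.40 to −2.33 | 19.8 | −2.17 | 11.3 | 77.8% to 75.4% | 69.3% |

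Power uses the normal approximation with 78 per arm, so these losses are taken as part of the 20% allowance.

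**Does the planned imputation help?** Model A was simulated with 1,000,000 per arm, an assumed baseline mean of 12, baseline SD 4.5 and baseline–change correlation −0.3. The week-6 model was adjusted for baseline. Observed-data analysis and regression imputation on group and baseline agree to within 0.003: both −2.46 at r = 0.5, q = 0.25; both −2.42 at r = 0.9, q = 0.25; both −2.33 at r = 0.9, q = 0.50. Imputation under MAR reproduces the shift.

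**No true effect (both means −3.0).** Equal q gives zero bias. As an illustration only, q = 0.25 in one arm and 0.10 in the other gives 0.14 (r = 0.5) to 0.25 (r = 0.9) in model A and 0.21 in model B. Type I error is then about 5.3% to 5.9%. Model B is not a bound for this case.

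**Larger imbalance.** A separate simulation (98 per arm, 4,000 runs) drew losses from the worst fifth of each arm. Losing 2% against 5% moved the estimate about 0.25 points, 5% against 10% about 0.45, and 0% against 10% about 0.85, with null rejection of about 6% to 6.6%, 9% to 9.6% and 19% to 20%. The sign follows whichever arm loses more. Equal losses left the estimate at about 2.50.

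**The case against.** The case on the other side is that 9.2 is discretionary and silent, while the plan leans toward retention: ITT on everyone randomised, remote follow-up in 10.3(5), adverse-event follow-up in 9.1, and the bar on exclusions in 10.4.6. Rescue celecoxib (7.4) and the exclusion of patients with surgical indications (4.3) should keep such withdrawals few. A MAR-based MMRM with MAR imputation is a common plan, and the SAP may still be finalised before database lock (11.2). Every rate above is assumed.

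Most of this stands, and it is why the point is minor. It does not remove the gap. An investigator's withdrawal is not poor compliance, 9.1 concerns adverse events, and 10.4.6 governs exclusion from analysis rather than scores never collected. That a delta analysis could be added later does not make it planned.

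Four stronger readings are tempting, and the documents do not support them:
- *Section 9.2 forbids further data collection.* It does not say so, and the consent form was not available for this review.
- *No remote route exists at week 6.* The notebook wording in 10.5(5) suggests this, but 10.3(5) is not tied to any visit.
- *Sections 5.2 and 7.4 force out a worsening patient who needs other therapy.* Section 5.2 is firm ("it is imperative that patients avoid any therapy for DLSS throughout the trial"), but 7.4 is softer ("The use of medications or other therapies specific for symptoms of DLSS will be discouraged during this trial"). Nowhere is other therapy a ground for withdrawal, and 10.4.4 provides for coding concomitant medication.
- *The result is biased in favour of acupuncture.* That needs unequal withdrawal. Section 6.2 states: "Only acupuncturists are aware of the group allocation to administrate treatments". Nothing shows that withdrawal would differ by arm.

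**Conclusion.** The point holds as a minor one. As written, the plan allows a week-6 RMDQ to be lost for a reason tied to the outcome, and neither the MMRM nor the MAR imputation can test the consequence.

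Under one common rule with a true 2.5-point benefit, the shift is toward no effect: 0.04 to 0.15 points if 25% of worsening patients are withdrawn and 0.10 to 0.33 at 50%, against an SE of 0.88. With no true effect and equal application it is zero.

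These sizes rest on assumed withdrawal rates, an assumed worsening threshold and the two selection models. Calling the effect small also assumes that the arms differ by no more than about 3 to 5 percentage points in such withdrawals. A gap of 10 points would matter, but the documents give no reason to expect one. The sample-size calculation is not affected.

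**What to change.** 1. **Protocol 9.2.** State that the investigator's decision ends study treatment only. Participants still complete RMDQ, NRS, SSSQ and HADS at weeks 6, 18 and 30 unless they withdraw consent to follow-up. Say that the existing phone or message route in 10.3(5) applies to them. Record the mode of collection, the reason and date of stopping, and any other DLSS therapy.
2. **SAP 6.3.3.** Add a delta-adjusted tipping-point analysis for values still missing at week 6, varied separately by arm. For example, add 0, 2.5, 5, 7.5 and 10 points to the MAR-imputed change, cap the resulting score at 24, and report where the conclusion changes. The grid fits the models: for q from 0.10 to 0.50, withdrawn patients are about 3.7 to 8.1 points worse than those who stay in model A, and from 8.5 to just under 11 in model B.

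The cost is a few sentences in 9.2, one SAP paragraph before database lock and code breaking, and remote week-6 contacts by existing assessors. These would number about 2 to 10 participants if 10% to 25% of worsening patients stop, and about 11 to 20 at 50%. The downsides are that a few week-6 scores are collected remotely and some reflect other therapy. N stays at 196.
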